#### 7.1.6 Study Intervention

Will begin once 6-8 participants are assigned to intervention CONFIDENTIAL

This material is the property of the NYU School of Medicine and NYU Langone Health. Do not disclose or use except as authorized in writing by the study sponsor

Study number: s20-01911 Page 10 Version date: 3/8/2022

Administered over 8 weeks (see section 6 for details)

#### 7.1.7 Mid-intervention/M1

- Expected to be completed in 15 minutes halfway through the intervention
- Surveys via REDCap (see section 7.2.1.5 and 7.2.1.6 for details)

#### 7.1.8 Post-intervention/M2

- Expected to be completed in 30-45 minutes, within two weeks of intervention completion
- Surveys via REDCap (see section 7.2.1.5 and 7.2.1.6 for details)
- A sub-sample of participants with varying levels of engagement with the study (approximately 3-4 from each cohort) will be invited to provide post-intervention individual qualitative feedback about the feasibility and acceptability of the study procedures and intervention

#### 7.1.9 M3

- Expected to be completed in 30-45 minutes, within +/- 2-week of 3 months since baseline
- Surveys via REDCap (see section 7.2.1.5 and 7.2.1.6 for details)
- A sub-sample of participants with varying levels of engagement with the study (approximately 3-4 from each cohort) will be invited to provide post-intervention individual qualitative feedback about the feasibility and acceptability of the study procedures and intervention

#### 7.1.10 M6

- Expected to be completed in 30-45 minutes, within +/-2-week of 6 months since baseline
- Surveys via REDCap (see section 7.2.1.5 and 7.2.1.6 for details)
- A sub-sample of participants with varying levels of engagement with the study (approximately 3-4 from each cohort) will be invited to provide post-intervention individual qualitative feedback about the feasibility and acceptability of the study procedures and intervention

#### 7.1.11 M9

- Expected to be completed in 30-45 minutes, within +/- 2-week of 9 months since baseline
- Surveys via REDCap (see section 7.2.1.5 and 7.2.1.6 for details)
- A sub-sample of participants with varying levels of engagement with the study (approximately 3-4 from each cohort) will be invited to provide post-intervention individual qualitative feedback about the feasibility and acceptability of the study procedures and intervention

# 7.2 Study Procedures and Evaluations

#### 7.2.1 Study Specific Procedures

#### 7.2.1.1 Further Eligibility Screening

Individuals who meet pre-screening eligibility and who are interested in taking part in this study will be provided with e-Consent materials (hosted on REDCap) and will be scheduled to meet with a Research Assistant via telephone or video to review e-Consent materials, answer questions, and confirm understanding of the study procedures. If still interested, the subject will electronically sign the e-Consent and a pdf copy will be provided to them.

Individuals who meet preliminary eligibility criteria and who consent to participation in this study will stay on the call for further eligibility screening (20-40 minutes). During this eligibility interview, study staff will:

Study number: s20-01911 Page 11 Version date: 3/8/2022

Conduct a structured interview and then review responses with the study neurologist at each site to

ascertain whether the subject meets ICHD-3 criteria for migraine using the American Migraine

• Administer the PHQ-9 to assess depression and suicidality

Prevalence and Prevention Diagnostic Module

Ask additional eligibility questions as outlined in the "Phone Screener" document

Drs. [name], [name], [name], [name], and [name] will provide supervision at their respective sites on depression and migraine inclusion/exclusion criteria and will be available to address any questions regarding these criteria.

Subjects who pass this eligibility assessment will be assigned to an intervention and scheduled for a 30-minute individual orientation session with the intervention facilitator.

#### 28-Day Baseline Run-In

Participants who meet preliminary criteria and provide informed consent will complete a 28-day baseline run-in to ensure participants meet inclusion/exclusion criteria for migraine diagnosis and the threshold for minimal diary adherence (25/28 days). During the baseline run-in, participants will complete a daily diary including headache symptoms using the REDCap Mobile App or Gene Doe app. If participants do not have a personal device, one will be provided by the research team. The application will prompt a diary entry at a time selected by the participant each evening. If a patient does not submit a daily entry, they will be alerted that the diary entry is still waiting for 12 hours. Participants will not be permitted to record retrospective data to reduce recall bias. Participants who continue to meet inclusion/exclusion criteria after the 28-day baseline run-in will be randomized to receive either 8 sessions of MBCT-T, MBCT-V, or Enhanced Usual Care.

#### 7.2.1.2 Randomization

Randomization will be stratified by headache days [low-frequency episodic migraine (4-9 days/28 days), high-frequency episodic migraine (10-14 days/28 days)] and gender (male, female). A randomization list will be generated by the study statistician using randomization within random blocks of sizes 3 and 6. Participants will be masked to intervention options and study hypotheses. They will be informed that they will be randomized to one of three interventions that will last a maximum of 8 weeks and that will provide knowledge to help migraine and depressive symptoms. Facilitators will be unmasked. Data will be entered and coded so that group membership is known only to the project coordinator at NYULH and to research assistants who are coordinating study visits. The graduate research assistant who will be coordinating data capture across sites, as well as the investigators, will be masked to treatment condition.

# 7.2.1.3 8-Week Intervention Program

### 7.2.1.3.1 MBCT-T/V

Both MBCT-T and MBCT-V will be delivered using WebEx conferencing, which allows for a 'call-in' option that does not require internet for the MBCT-T arm. MBCT-T/V will be delivered to groups of 8 migraine patients in 8 weekly, 1-hour sessions. Smartphone devices with unlimited data plans will be available for participants who need them to participate in the study both to complete the headache diary (see below for details) and if they are randomized to either remote-delivered intervention. Our team has used the WebEx platform for three clinical trials and will ensure that all facilitators and research support staff are trained and that a comprehensive manual is available to help troubleshoot potential technical difficulties. At least one research assistant will join each weekly session to help assist with any technical difficulties participants may have. Unforeseen difficulties with the technology will provide us with additional information about the feasibility of this intervention.

Critical components of MBCT include: 1) learning mindfulness skills; 2) practicing mindfulness skills in class and at home; and 3) dialogue and inquiry. The intervention manual will be an adapted version of [name] remote-delivered MBCT for chronic pain protocol (i19-00339) and [name] in-person MBCT for migraine

Study number: s20-01911 Page 12 Version date: 3/8/2022

protocol. All sessions will be audio-recorded. Patients will be encouraged to practice daily meditation in between group sessions for 20 minutes, 6 days per week.

As a headache diary is a core component of all headache treatments, participants will complete a daily headache diary, which will include recording of daily meditation practice. To maximize adherence and retention, coordinators will give reminder calls to patients prior to each weekly class and will contact patients who miss a weekly session to schedule a make-up session, whereby patients can listen to the audio recording of the missed session.

Table 1. Structure and Content of MBCT-T and MBCT-V		
Structure	Weekly Content	
Homework review (except session 1)	1. Awareness & Automatic Pilot	
	2. Awareness of the Body	

 
In-session practice of both meditation-based and
 
	3. Thoughts are not Facts	
cognitive-behavioral exercises	4. Gathering the Scattered Mind	
Guided inquiry	5. Allowing/Letting Be	
Summary of main themes and assign at-home daily	Awareness of Warning Signs     Reactivity	
practice	7. Taking Care of Myself	
	8. Maintenance	

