# 7.2.1.3.2 EUC

Participants randomized to EUC will receive usual care and 8 weekly online education modules whose delivery and content are based on control groups from previous behavioral migraine and depression interventions. Modules will be released on a weekly basis, which mirrors the MBCT arms. Participant engagement with each

Version date: 3/8/2022

module happens individually (not in a group) and will be tracked electronically by the secure hosting website. Participants will also complete a daily headache diary.

Table 2. Structure and Content of EUC		
Structure	Weekly Content	
Online module accessed through weblink	1. What is Migraine?	
Multi-tab structure leading	2. Migraine and Depressive Symptoms	

participant through education

Low health literacy definitions

	3. Migraine, Depressive Symptoms and the Brain	
of key concepts	4. Diagnosis of Migraine and Depression	

 
Application of key concepts to the person with migraine and depressive symptoms
 
	5. Treatment Options for Migraine and Depression	
Vignettes depicting people with migraine and depressive	6. Impact of Migraine and Depressive Symptoms	
symptoms demonstrating key concepts	7. Lifestyle Factors for Migraine and Depressive Symptoms	
	8. Communicating with Health Care Providers	

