#### 7.2.1.4 Assessments

Please see Table 3 for an overview of assessment timeline and sections 7.2.1.6 and 7.2.1.7 for details.

Subjects will be asked to complete questionnaires online via REDCap, via REDCap Mobile App, or via Gene Doe App, (or on paper if they prefer – we will mail subjects the questionnaires).

Table 3. Schedule of Assessments

	Data collection by study personnel	Assessments completed by participants
Pre-Screening		Online Pre-screener
Screening	Recruitment Rate	Phone Screener
•	Daily Diary Completeness	Headache frequency
M-1^		Demographics
		FFMQ-15
		HMSES
		CEQ
		QIDS
		PROMIS
		Off-Protocol Co-Occurring Treatment Tracking
		HDI
		MSQ
		Survey Acceptability Questionnaires-7
Daily Diary		Headache frequency
(M-1 - M3)		Average Headache Attack Pain Intensity
M0*	Survey Completeness	SUS-Data Capture
	Daily Diary Completeness	HDI
		QIDS
		PROMIS-D
		MSQ

		HMSES
		MAIA-2
		PCS HPAQ
		MIDAS
Weekly During	Treatment Session Adherence	Safety Tracking
Intervention	Fidelity Checklist Survey Completeness	Homework Assignment Adherence
M1**	Survey Completeness	QIDS
	Daily Diary Completeness	PROMIS-D
	Attrition	HDI
		MSQ MBCT-HPI
		MAIA-2
		PCS
		HPAQ
		MIDAS
		Survey Acceptability Questionnaires-7
M2***	MBCT-TACS	CSQ-8
	Survey Completeness	FFMQ-15
	Retention Rate Survey Completeness	HMSES SUS-Treatment
	Daily Diary Completeness	QIDS
	Attrition	PROMIS-D
		Off-Protocol Co-Occurring Treatment Tracking
		HDI
		MSQ
		MBCT-HPI MAIA-2
		PCS
		HPAQ
		MIDAS
		For some: M2 Qualitative Questions (Exit
1400		interview)
M3°	Survey Completeness Daily Diary Completeness	CSQ-8 MBCT-HPI
	Attrition	SUS-Data Capture
	, and an	HDI
		QIDS
		PROMIS-D
		MSQ
		MAIA-2 PCS
		HPAQ
		MIDAS
		Survey Acceptability Questionnaires-7
M6°°	Survey Completeness	CSQ-8
	Attrition	MBCT-HPI
		SUS-Data Capture HDI
		QIDS
		PROMIS-D
		MSQ
		MAIA-2
		PCS
		HPAQ MIDAS
M9°°°	Survey Completeness	CSQ-8
	Attrition	MBCT-HPI
		HDI
		QIDS
		PROMIS-D

Version date: 3/8/2022

	MSQ MAIA-2
	PCS
	HPAQ
	MIDAS
As Needed	BSS

^ M-1 = Month -1/Baseline; \* M0 = Month 0/Pre-Intervention; \*\* M1 = Month 1/Mid-Intervention; \*\*\* M2 = Month 2/Post-Intervention; ° M3 = Month 3 (1 Month Post-Intervention); ° M6 = Month 6 (4 Months Post-Intervention); °° M9 = Month 9 (7 Months Post-Intervention)

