Name: System Usability Scale (SUS): Treatment

Type: Secondary

Time Frame: M2

Brief Description: The SUS for Treatment is a measure of treatment acceptability. The SUS is a 10-item

scale that assesses end-user perceived usability of information technology systems. For the current scale, the system being evaluated will be the WebEx system for treatment delivery for both the MBCT-T (no internet connection required) and MBCT-V arms of the study, and the online education platform used for the EUC arm of the study. Response options range from 1-5; half of the items are positively worded, and

Version date: 3/8/2022

half are negatively worded. Scores are converted to a score ranging from 0-100 with higher scores indicating higher perceived usability.

Name: System Usability Scale (SUS): Data Capture

Type: Secondary
Time Frame: M3, M6

Brief Description: The SUS for Data Capture is a measure of acceptability of study procedures. The

SUS is a 10-item scale that assesses end-user perceived usability of information technology systems. For the current scale, the system being evaluated will be the mobile application used for data capture for surveys and daily diary. Response options range from 1-5; half of the items are positively worded, and half are negatively worded. Scores are converted to a score ranging from 0-100 with higher

scores indicating higher perceived usability.

Name: Beck Suicide Scale (BSS)

Type: Secondary

Time Frame: As needed - the measure is administered any time an individual indicates a presence

of suicidal thoughts on either the PHQ-9 or the QIDS-16 or in between assessments

to anyone on the study team.

Brief Description: This is a standard 21-item scale that members of the research team have used in prior

trials to assess risk of suicide. The BSS indexes current intensity of attitudes, plans, and behaviors to complete suicide. Scores over 11 and/or endorsement of a '2' on any of the following items 12, 15, 16, 18, and 21 indicate notable risk. See Appendix 1 for

suicide safety protocol.

Name: Safety Tracking Type: Secondary

Time Frame: Intervention. The measure is administered via survey and RA check-ins by telephone

(mid-way through the intervention period) at Months 1 and 2. Total number of Adverse Events (AEs) and Serious Adverse Events (SAEs) will be evaluated.

Brief Description: AE and SAE data will be collected through surveys and by RAs. Surveys include

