standardized inventories that measure anticipated adverse events, including anxiety, flooding, depersonalization, and dissociation, as well as an open-ended question about any other troublesome medical occurrences. RA check-ins (mid-way through the intervention period) will involve inquiry about migraine and depressive symptom deterioration and suicidal ideation. An adverse event (AE) is any troublesome medical occurrence in a subject during participation in the clinical study. A serious adverse event (SAE) is any AE that results in one or more of the following outcomes: death, a life-threatening event, inpatient hospitalization or prolongation of existing hospitalization, a persistent or significant disability/incapacity, a congenital anomaly or birth defect, or an important medical event based upon appropriate medical judgment. We will use the HHS/NIH/NCI Common Terminology Criteria for Adverse Events (Version 4.0) grading scale. The RA(s), neurologist Co-I and PI will work

together to determine AEs and SAEs.

Name: Homework Assignment Adherence

Type: Secondary Time Frame: Intervention

Brief Description: Homework assignment adherence is a measure of treatment feasibility. During the

intervention period, participants in the MBCT groups will be asked to record the

amount of assigned home-based practice they completed each day.

Name: Survey Acceptability Questions

Type: Secondary
Time Frame: M0, M1, M2

Version date: 3/8/2022

Brief Description: The Acceptability Questions are a measure of treatment acceptability and are to be

administered at the end of each time point. 7 questions assess perceived

acceptability of preceding surveys. Response options for questions 1-6 range from Strongly Disagree to Strongly Agree on a 4-point Likert Scale. Question 7 is open-

ended to allow for free-form participant responses.

Name: Qualitative Questions

Type: Secondary

Time Frame: M2

Brief Description: Some participants (approximately 3-4 from each cohort) will be invited to provide

post-intervention qualitative feedback about the feasibility and acceptability of the study procedures and intervention. Questions are open-ended and cover topics

related to the questionnaires, study procedures, and intervention.

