# 8.3 Time Period and Frequency for Event Assessment and Follow-Up

The occurrence of an AE or SAE may come to the attention of study personnel during study visits and interviews of a study participant presenting for medical care, or upon review by a study monitor. All AEs including local and systemic reactions not meeting the criteria for SAEs will be captured on the appropriate RF. Information to be collected includes event description, time of onset, clinician's assessment of severity, relationship to study intervention (assessed only by those with the training and authority to make a diagnosis), and time of resolution/stabilization of the event. All AEs occurring while on study must be documented appropriately regardless of relationship. All AEs will be followed to adequate resolution.

Any medical condition that is present at the time that the participant is screened will be considered as baseline and not reported as an AE. However, if the study participant's condition deteriorates at any time during the study, it will be recorded as an AE. UPs will be recorded in the data collection system throughout the study.

Changes in the severity of an AE will be documented to allow an assessment of the duration of the event at each level of severity to be performed. AEs characterized as intermittent require documentation of onset and duration of each episode.

The PI will record all reportable events with start dates occurring any time after informed consent is obtained. SAEs will be followed until resolutions are reached as stated below. AEs will be followed for the duration of an individual's participation in the study. At each study visit, the investigator will inquire about the occurrence of AE/SAEs since the last visit. Events will be followed for outcome information until resolution or stabilization.

All unresolved adverse events should be followed by the investigator until the events are resolved, the subject is lost to follow-up, or the adverse event is otherwise explained. At the last scheduled visit, the investigator should instruct each subject to report any subsequent event(s) that the subject, or the subject's personal physician, believes might reasonably be related to participation in this study. The investigator should notify the study sponsor of any death or adverse event occurring at any time after a subject has discontinued or terminated study participation that may reasonably be related to this study.

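### An all-source adverse-event total may show a modest MBCT excess from detection alone, because only the MBCT arms add weekly live contact to the safety collection common to all arms, and event source is not recorded

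*Combined protocol and SAP*

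**What the plan says.** **Collection with no arm restriction.** The Safety Tracking entry in Section 7.2.1.5 defines the outcome: "Total number of Adverse Events (AEs) and Serious Adverse Events (SAEs) will be evaluated". On sources it says "AE and SAE data will be collected through surveys and by RAs", and on method "The measure is administered via survey and RA check-ins by telephone", with Months 1 and 2 as the time points. The surveys include inventories for anxiety, flooding, depersonalization and dissociation, plus an open-ended question. "RA check-ins (mid-way through the intervention period) will involve inquiry about migraine and depressive symptom deterioration and suicidal ideation". Table 3 (Section 7.2.1.4) lists "Safety Tracking" in the weekly row of the intervention period. Section 8.1 promises weekly depressive-symptom monitoring, Section 8.3 has the investigator ask about AEs at each study visit, and Section 2.3.1 says EUC participants are followed similarly.

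**Contact in the MBCT arms only.** Section 7.2.1.3.1 provides eight weekly one-hour group sessions, a reminder call before each class and a call after a missed one. It adds: "At least one research assistant will join each weekly session to help assist with any technical difficulties participants may have". Section 7.1.4 gives MBCT participants a 30-minute orientation with the facilitator. Section 2.3.1 has the facilitator act on severe depressive symptoms or suicidal ideation reported during the intervention. In EUC, Section 7.2.1.3.2 describes online modules that each participant works through alone.

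**What enters the record and the analysis.** Section 8.3 says "The occurrence of an AE or SAE may come to the attention of study personnel during study visits and interviews" and requires all on-study AEs to be documented. Section 9.1 (Planned Secondary Analyses) groups AEs with the monthly-survey outcomes, which are modelled across the three arms.

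**The concern.** A comparison of AE counts between arms is interpretable only if the arms have a similar chance of having an event noticed. Here the structured channels are common, but the MBCT arms have a second route: participants talk every week with a facilitator, in front of an RA, in sessions where discussing negative emotions is part of the treatment. An event that the surveys and the check-in miss can still be voiced there and, under Section 8.3, must then be documented. An EUC participant has no matching weekly occasion.

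If the total is compared across arms without knowing how each event was found, a modest MBCT excess cannot be divided into harm and detection. The trial is meant to inform a Phase III design, and the source of an event is hard to recover reliably afterwards.

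**Working it through.** The documents give no AE rate and no sample size or power for AEs, so there is no figure of the plan's own to reproduce.

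**Step 1. Scheduled live contacts beyond the common channels.** MBCT: 8 sessions + up to 8 reminder calls + 1 orientation = up to 17 per participant, plus any missed-session calls. EUC: 0 of these.

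**Step 2. Which events are analysed?**

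| Place | Source or frequency |
|---|---|
| 7.2.1.5, Safety Tracking | Surveys and RAs; Months 1 and 2 |
| 7.2.1.4, Table 3 | Weekly during the intervention; not listed in the M1 or M2 rows |
| 9.1, Planned Secondary Analyses | Monthly survey |
| 8.3 | Every on-study AE documented |

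These do not define one set of events. If the arm comparison follows Section 9.1 literally, volunteered events are outside it. If it follows the total in Section 7.2.1.5, events that reach an RA in a session or a call can be inside it.

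**Step 3. Possible size.** Assume equal true incidence in all arms. Let s be the share of events caught by the common channels, and u the share of the remainder caught by MBCT-only contact. Both are assumptions. Per participant, the recorded share is s in EUC and 1 − (1 − s)(1 − u) in MBCT, so

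ratio = [1 − (1 − s)(1 − u)] / s = 1 + u(1 − s)/s.

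| s | u = 0.1 | u = 0.3 | u = 0.5 |
|---|---|---|---|
| 1.0 | 1.00 | 1.00 | 1.00 |
| 0.9 | 1.01 | 1.03 | 1.06 |
| 0.7 | 1.04 | 1.13 | 1.21 |
| 0.5 | 1.10 | 1.30 | 1.50 |

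For the last cell: 1 + 0.5 × 0.5/0.5 = 1.50.

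**Step 4. Chance of a falsely significant MBCT excess.** Section 9.1 gives 144 participants allocated 1:1:1, so 96 in the two MBCT arms and 48 in EUC, and two-sided 0.05 tests. As an illustration (the plan does not specify this test), take Poisson counts and an exact binomial test conditional on the total, with null share 96/144 = 2/3. With one true AE per participant, expected counts are 96 × [1 − (1 − s)(1 − u)] and 48 × s:

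| s | u | MBCT | EUC | Chance of a significant MBCT excess |
|---|---|---|---|---|
| 1.0 | 0 | 96.0 | 48.0 | 0.022 |
| 0.9 | 0.3 | 89.3 | 43.2 | 0.032 |
| 0.7 | 0.3 | 75.8 | 33.6 | 0.072 |
| 0.5 | 0.3 | 62.4 | 24.0 | 0.171 |
| 0.5 | 0.5 | 72.0 | 24.0 | 0.393 |

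With 0.5 true AEs per participant the last row becomes 0.195; with 2 it becomes 0.695. The first row also shows that pooled MBCT counts are twice the EUC count with no difference at all, so raw totals need a per-participant denominator.

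**The case against.** The case on the other side is substantial.

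- **Common ascertainment is good.** The harms most expected of MBCT are asked about by standardised inventory and an open question, backed by an RA call and weekly monitoring, none of it limited by arm. Bias can come only from events that all of these miss. This stands, and it makes the upper rows of the ratio table more plausible than the bottom one.
- **The RA in the session is there for technical help.** This stands too. The sentence shows that staff are present, not that AEs are asked about. Section 8.3 does not name treatment sessions as a source, and the facilitator duty in Section 2.3.1 covers only severe symptoms and suicidal ideation. The route is incidental, but Section 8.3 requires no formal inquiry before an event is documented.
- **Section 9.1 may already confine the comparison to survey events.** If so, the concern largely falls away. But the section does not say that it excludes RA-collected events, and Section 7.2.1.5 includes them.
- **No decision rule uses AEs.** Correct: they appear in none of the Aim 2 benchmarks or superiority criteria.
- **Dropping volunteered events could hide real harm.** Correct: Section 2.3.1 names destabilising experiences during meditation as a risk. An all-source total must therefore stay beside any restricted comparison.

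A reader might infer that EUC participants have no staff contact through which AEs could be found. The documents do not support that: what EUC lacks is scheduled weekly live contact, not safety follow-up.

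**Conclusion.** The point holds as a minor one. Detection opportunity differs between arms in a known direction, the source of an event is not recorded, and the sections disagree on which AEs are analysed. An all-source total may therefore show a modest MBCT excess without any true difference.

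The size is unknown. The range of 1.00 to 1.50 rests on assumed capture shares and equal true incidence; at 90% common capture it is only 1.01 to 1.06. The error rates also assume Poisson counts and pooled MBCT arms.

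A reader might infer that any MBCT excess would be an artefact, or that the total is biased by a particular factor. Neither follows: the documents contain no capture rate, and an excess could be real. Nor is the pilot's go/no-go conclusion threatened, since AEs do not enter it.

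**What to change.** 1. Add an AE source field to the CRF: survey, scheduled RA check-in, volunteered in a session or call, other. Count an event reported by both a solicited and a volunteered route once, as solicited.
2. In Section 7.2.1.5 (Safety Tracking) and Section 9.1 (Planned Secondary Analyses), make the main between-arm comparison the per-participant incidence of events from the channels given identically to all arms. Report beside it the all-source total by arm and the volunteered events by arm.
3. Reconcile the Safety Tracking frequency between Table 3 (weekly) and Section 7.2.1.5 (Months 1 and 2).

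The cost is one CRF field, a short addition to the analysis text and fewer events in the main comparison. That comparison may under-count harms voiced only in sessions, which is why the all-source total is kept. Handling and reporting of individual events do not change.
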